2. INTRODUCTION

Variable domain of a heavy-chain-only antibody (VHH) fragments are the antigen-binding units derived from heavy chain only camelid antibodies. Compared to conventional antibodies or antibody fragments, VHH fragments are smaller (15 kDa) and they have the ability to bind antigens on hidden or unusual epitopes. VHHs are considered low immunogenic, have nanomolar affinities and can be produced in high yields (1).

Malignant tumors are characterized by the presence of specific proteins on their cell membrane. These cancer antigens are expressed in relatively high amounts and often their expression level is related to a signal transduction cascade that contributes or promotes the cancer phenotype. Hence, these membrane antigens represent an important target for anti-cancer treatment. Theoretically, VHHs can be generated against virtually any cancer-specific membrane-associated protein. In a series of studies, the In vivo Cellular and Molecular Imaging lab (ICMI) at the Vrije Universiteit Brussel (VUB) demonstrated that VHHs bear unusually beneficial properties for targeted radionuclide therapy (TRNT) (2-4). Indeed, in mice, radiolabeled VHHs efficiently penetrate tumors and tissues; bind biomarkers expressed on cells very fast and very specifically while unbound VHH is rapidly cleared from non-target organs and tissues. When coupled to a diagnostic radionuclide, this allows generating high contrast images as fast as 1h after tracer administration (5). As such the ICMI lab has developed them as efficient radiotracers for diagnostic imaging in various animal models of cancer, inflammation and cardiovascular diseases using Single Photon Emission Computed Tomography (SPECT) or Positron Emission Tomography (PET) (6-8).

The human epidermal growth factor receptor type 2 (HER2) is a typical example of a membrane receptor that is highly expressed on the cell membrane of breast and ovarian carcinoma. Signaling of this receptor causes cell proliferation, enhances cell mobility and reduces apoptosis. Consequently, HER2 over-expression is associated with tumor aggressiveness and an increased probability for recurrent disease. Targeted therapies for HER2 over-expressing tumors are currently available, such as monoclonal antibodies (Trastuzumab and Pertuzumab) that specifically bind the extracellular domain of HER2, and specific tyrosine kinase inhibitors (lapatinib) that interact with the intracellular domain of HER2. Information on the HER2 status of tumors is therefore of great importance since it has an enormous impact on the selection of the patients' therapy. At present, HER2 expression is assessed using tissue biopsies. The Anti-HER2 VHH1 was selected as a lead compound because of superior characteristics and the fact that it does not compete with binding of Trastuzumab and Pertuzumab (7).

The Anti-HER2 VHH1 was successfully evaluated in a first clinical study: the UZBRU-VHH1 study. In this study the Anti-HER2 VHH1 was labeled with [⁶⁸Ga] to non-invasively detect HER2 expression using PET. The evaluation of safety and tolerability as primary outcome,

CAMEL-IDS NV [name] www.camel-ids.com

Page 9 of 36

based on observed adverse events (AEs), was completed for all 20 patients. No related AEs were observed. The main conclusions of the HER2 diagnostic clinical study are that (i) [⁶⁸Ga]-HER2 PET/CT is a safe procedure with a radiation dose comparable to other PET/CT procedures and (ii) the radiolabeled VHH imaging reveals whole-body expression of HER2 in primary tumors and metastases.

Preclinical studies with the Anti-HER2 VHH1 labeled with [¹³¹I] were performed. In these studies the compound revealed similar binding characteristics and *in vivo* blood clearance compared to the [⁶⁸Ga]-labeled compound. However, the biodistribution profile was more favorable with much lower kidney values compared to the [⁶⁸Ga]-labeled compound in mice. The dose delivered to the tumor remained high and was higher than the dose delivered to the kidneys. The favorable biodistribution in mice of [¹³¹I]-SGMIB Anti-HER2 VHH1, combined with the theranostic characteristics of [¹³¹I] has now triggered the interest to use this compound as a therapeutic agent in TRNT of cancer (9-10).

The rationale for the development of [¹³¹I]-SGMIB Anti-HER2 VHH1 is to allow both screening patients for the presence of the HER2 antigen using SPECT and a subsequent therapeutic approach using the identical compound (11). The screening approach will offer superior diagnostic performance because the entire tumor lesion as well as possible metastatic lesions can be evaluated with a single total body scanning procedure (SPECT). The procedure is fast, painless and sampling errors with biopsies are avoided. This screening test will allow the clinician to select patients that are susceptible to TRNT. In patients that do not have HER2 positive cancers unnecessary, expensive and potentially toxic treatment can be avoided. The SPECT scans could also be used to follow the expression of this biomarker during the disease process and act as prognostic marker.

CAMEL-IDS NV [name] www.camel-ids.com

Page 10 of 36

3. STUDY OBJECTIVES

Part I

Primary objectives of the clinical study:

1. To evaluate the safety, biodistribution and radiation dosimetry of $[^{131}I]$ -SGMIB Anti-HER2 VHH1 in 6 healthy volunteers

Part II

Primary objectives of the clinical study:

1. To evaluate the safety and biodistribution of [¹³¹I]-SGMIB Anti-HER2 VHH1 in 4 patients with HER2+ breast cancer.

Secundary objective of the clinical study:

2. To evaluate the tumor uptake of [¹³¹I]-SGMIB Anti-HER2 VHH1 in 4 patients with HER2+ breast cancer.

4. STUDY DESIGN

Single center, open, non-randomized first-in-man clinical trial

5. INVESTIGATIONAL PLAN

5.1 Overall Study Design

Single center, open, non-randomized first-in-man clinical trial

5.2 Study groups

This study will be conducted in 2 parts.

Part I is in healthy volunteers to demonstrate the safety and to assess the biodistribution and human dosimetry of [¹³¹I]-SGMIB Anti-HER2 VHH1.

If Part I is successful according to the Data Safety Monitoring Board (DSMB) decision, Part II will be initiated. The composition, role and procedures of the DSMB will be described in the DSMB charter.

Part II is in patients with HER2+ breast cancer to demonstrate the safety and to assess the biodistribution and tumor uptake of [¹³¹I]-SGMIB Anti-HER2 VHH1.

All subjects will receive only one single intravenous injection of the investigational medical product (IMP).

CAMEL-IDS NV [name] www.camel-ids.com

5.3 Time schedule

First subject: December 2015 Last subject: January 2018

5.3.1 Part I (Healthy volunteers)

An overview of the investigational actions for each subject in Part I of the study can be found in Table 1.

The individual subject schedule will be:

Visit 1: screening and inclusion

-Informed consent

-Inclusion / exclusion criteria

-Medical history

-Information about subject preparation: 6±2h fasting at administration of [¹³¹I]-SGMIB Anti-HER2 VHH1.

-Information about oral administration of 130 mg potassium iodide for thyroid blockade: potassium iodide dosed as 1 ingestion daily starting 24±6h before [¹³¹I]-SGMIB Anti-HER2 VHH1 administration and continued until 48±12h after administration of [¹³¹I]-SGMIB Anti-HER2 VHH1.

Visit 2: 1 day before administration

-Information about subject preparation: 6±2h fasting at administration of [¹³¹I]-SGMIB Anti-HER2 VHH1.

-First ingestion of 130 mg potassium iodide

-Blood sampling for HCG test unless postmenopausal for 2 years.

-Blood sampling for biochemical analysis: hematology, liver enzymes and renal function (urea, creatinine). Blood will be collected in dry Li-Heparin and EDTA tubes (S-Monovette®, Sarstedt). Samples will be analyzed for biochemical and hematological parameters.

Visit 3: baseline

• Pre-administration

-Physical exam including vital signs and medical history

-Second ingestion of 130 mg potassium iodide

-Blood sampling for activity measurement. Blood will be collected in a dry Li-Heparin tube (S-Monovette®, Sarstedt). 0.5 ml of blood will be pipetted in a counting tube, the remaining blood will be centrifuged and 0.5 ml of plasma will be put in a counting tube.

-Blood sampling for biochemical analysis: hematology, liver enzymes and renal function (urea, creatinin). Blood will be collected in dry Li-Heparin and EDTA tubes (S-Monovette®, Sarstedt). Samples will be analyzed for biochemical and hematological parameters.

CAMEL-IDS NV [name] www.camel-ids.com

-An intravenous line will be inserted in an anticubital vein for administration of the product and a similar venous access will be installed in a different vein of the opposite arm for blood sampling. A saline infusion of 250 ml will be administered before administration of [¹³¹I]-SGMIB Anti-HER2 VHH1.

• Administration

-IV-injection of [¹³¹I]-SGMIB Anti-HER2 VHH1 using an infusion pump within 5±3min.

-The empty syringe and intravenous line need to be removed and measured for residual radioactivity

-Remark: the study subject will not be allowed to urinate before the completion of total body planar scan 1 (t= 40 ± 10 min p.i.). In case the study subject could not withhold, urine should be collected and scanned with the subject during total body planar scan 1.

• Post-administration

-Dynamic scan kidneys & liver (gamma camera): $t = 0.30 \pm 10 \text{min p.i.}$

-Vital signs 5±10min p.i.

- Blood sampling for activity measurements: 5±3min-p.i

Blood will be collected in a dry Li-Heparin tube (S-Monovette®, Sarstedt). 0.5 ml of blood will be pipetted in a counting tube, the remaining blood will be centrifuged and 0.5 ml of plasma will be put in a counting tube.

- Blood sampling for activity measurements and metabolite analysis: 10±3min-p.i

Blood will be collected in a dry Li-Heparin tube (S-Monovette®, Sarstedt). 0.5 ml of blood will be pipetted in a counting tube, the remaining blood will be centrifuged and 0.5 ml of plasma will be put in a counting tube. The remaining plasma will also be used for HPLC analysis. 1 ml of plasma will be filtered (0.45 μ m) and 0.5 ml will be injected on the HPLC.

- Blood sampling for activity measurements: 20±5min-p.i

Blood will be collected in a dry Li-Heparin tube (S-Monovette®, Sarstedt). 0.5 ml of blood will be pipetted in a counting tube, the remaining blood will be centrifuged and 0.5 ml of plasma will be put in a counting tube.

- Blood sampling for activity measurements: 30±5min-p.i

Blood will be collected in a dry Li-Heparin tube (S-Monovette®, Sarstedt). 0.5 ml of blood will be pipetted in a counting tube, the remaining blood will be centrifuged and 0.5 ml of plasma will be put in a counting tube.

-Total body planar scan 1: $t = 40 \pm 10 \min p.i$.

-Blood sampling for activity measurements and metabolite analysis: 60±15min p.i.

Blood will be collected in a dry Li-Heparin tube (S-Monovette®, Sarstedt). 0.5 ml of blood will be pipetted in a counting tube, the remaining blood will be centrifuged and 0.5 ml of plasma will be put in a counting tube. The remaining plasma will also be used for HPLC analysis. 1 ml of plasma will be filtered (0.45 μ m) and 0.5 ml will be injected on the HPLC. -Urine sample will be collected for metabolite analysis: 60±15min p.i.

1 ml of urine will be filtered (0.45 μ m) and 0.5 ml will be injected on the HPLC.

Page 13 of 36
_

-Blood sampling for activity measurements: 105±30min p.i.

Blood will be collected in a dry Li-Heparin tube (S-Monovette®, Sarstedt). 0.5 ml of blood will be pipetted in a counting tube, the remaining blood will be centrifuged and 0.5 ml of plasma will be put in a counting tube.

-Total body planar scan 2: $t = 120 \pm 30 \text{min p.i.}$

-Blood sampling for activity measurements and metabolite analysis: 225±30min p.i.

Blood will be collected in a dry Li-Heparin tube (S-Monovette®, Sarstedt). 0.5 ml of blood will be pipetted in a counting tube, the remaining blood will be centrifuged and 0.5 ml of plasma will be put in a counting tube. The remaining plasma will also be used for HPLC analysis. 1 ml of plasma will be filtered (0.45 μ m) and 0.5 ml will be injected on the HPLC. -Urine sample will be collected for metabolite analysis: 225±30min p.i

1 ml of urine will be filtered (0.45 µm) and 0.5 ml will be injected on the HPLC.

-Total body planar scan 3: $t = 240 \pm 30$ min p.i.

-at t=4.5±1h p.i.: physical exam including vital signs

-Discharge of the subject

Visit 4: 24h after injection of the [131]-SGMIB Anti-HER2 VHH1

-Third ingestion of the 130 mg potassium iodide

-Blood sampling for activity measurements and metabolite analysis: 23.75±4h p.i.

Blood will be collected in a dry Li-Heparin tube (S-Monovette®, Sarstedt). 0.5 ml of blood will be pipetted in a counting tube, the remaining blood will be centrifuged and 0.5 ml of plasma will be put in a counting tube.

-Blood sampling for biochemical analysis: hematology, liver enzymes and renal function (ureum, creatinine): 23.75±4h p.i. Blood will be collected in dry Li-Heparin and EDTA tubes (S-Monovette®, Sarstedt). Samples will be analyzed for biochemical and hematological parameters.

-Urine sample will be collected for metabolite analysis: 23.75±4h p.i.

1 ml of urine will be filtered ($0.45 \mu m$) and 0.5 ml will be injected on the HPLC.

-Total body planar scan 4: $t= 24\pm 4h$ p.i.

-Provide subject with the fourth potassium iodide dose to be taken at $48\pm12h$ after administration of [¹³¹I]-SGMIB Anti-HER2 VHH1.

-Discharge of the subject

Visit 5: 72h after injection of the [¹³¹I]-SGMIB Anti-HER2 VHH1

-Confirmation of the fourth ingestion of 130 mg potassium iodide (taken at 48±12h)

-Blood sampling for activity measurements and metabolite analysis: 71.75±4h p.i.

Blood will be collected in a dry Li-Heparin tube (S-Monovette®, Sarstedt). 0.5 ml of blood will be pipetted in a counting tube, the remaining blood will be centrifuged and 0.5 ml of plasma will be put in a counting tube. The remaining plasma will be also used for HPLC analysis. 1 ml of plasma will be filtered (0.45 μ m) and 0.5 ml will be injected on the HPLC. -Urine sample will be collected for metabolite analysis: 71.75±4h p.i.

1 ml of urine will be filtered (0.45 μ m) and 0.5 ml will be injected on the HPLC. -Total body planar scan: t= 72±4h p.i. -Discharge of the subject

5.3.2 Part II (Patients with HER2+ breast cancer)

An overview of the investigational actions for each patient in part II of the study can be found in Table 2.

The individual patient schedule will be:

Visit 1: screening and inclusion

-Informed consent

-Inclusion / exclusion criteria

-Medical history

-Information about patient preparation: 6±2h fasting at administration of [¹³¹I]-SGMIB Anti-HER2 VHH1.

-Information about oral administration of 130 mg potassium iodide for thyroid blockade: potassium iodide dosed as 1 ingestion daily starting 24±6h before [¹³¹I]-SGMIB Anti-HER2 VHH1 administration and continued until 48±12h after administration of [¹³¹I]-SGMIB Anti-HER2 VHH1.

Visit 2: 1 day before administration

-Information about subject preparation: 6±2h fasting at administration of [¹³¹I]-SGMIB Anti-HER2 VHH1.

-First ingestion of 130 mg potassium iodide

-Blood sampling for HCG test unless postmenopausal for 2 years.

-Blood sampling for biochemical analysis: hematology, liver enzymes and renal function (urea, creatinine). Blood will be collected in dry Li-Heparin and EDTA tubes (S-Monovette®, Sarstedt). Samples will be analyzed for biochemical and hematological parameters.

Visit 3: baseline

• Pre-administration

-Physical exam including vital signs

-Second ingestion of 130 mg potassium iodide

-Blood sampling for biochemical analysis: hematology, liver enzymes and renal function (urea, creatinin). Blood will be collected in dry Li-Heparin and EDTA tubes (S-Monovette®, Sarstedt). Samples will be analyzed for biochemical and hematological parameters.

-An intravenous line will be inserted in a vein or port-a-cath for administration of the product and for blood sampling. A saline infusion of 250 ml will be administered before administration of [¹³¹I]-SGMIB Anti-HER2 VHH1.

CAMEL-IDS NV [name] www.camel-ids.com

• Administration

-IV-injection of [¹³¹I]-SGMIB Anti-HER2 VHH1 using an infusion pump within 5±3min.

-The empty syringe and intravenous line need to be removed and measured for residual radioactivity

-Remark: the patient will not be allowed to urinate before the completion of total body planar scan 1 (t= 15 ± 10 min p.i.). In case the patient could not withhold, urine should be collected and scanned with the patient during total body planar scan 1.

• Post-administration

-Vital signs 5±10min p.i.

-Total body planar scan 1: $t=15\pm10$ min p.i.

-Blood sampling for activity measurements and metabolite analysis: 60±15min p.i.

Blood will be collected in a dry Li-Heparin tube (S-Monovette®, Sarstedt). 0.5 ml of blood will be pipetted in a counting tube, the remaining blood will be centrifuged and 0.5 ml of plasma will be put in a counting tube. The remaining plasma will also be used for HPLC analysis. 1 ml of plasma will be filtered (0.45 μ m) and 0.5 ml will be injected on the HPLC.

-Total body planar scan 2: t= 120±30min p.i.

-SPECT/CT scan of 1 region with a cancer lesion: $t=2.5\pm1h$ p.i. The region will be selected by the PI based on the total body planar scan 2. The PI can decide not to execute a SPECT/CT scan.

-at t=3±1h p.i.: physical exam including vital signs

-Discharge of the patient

Visit 4: 24h after injection of the [¹³¹I]-SGMIB Anti-HER2 VHH1

-Third ingestion of 130 mg potassium iodide

-Blood sampling for biochemical analysis: hematology, liver enzymes and renal function (ureum, creatinine): 23.75±4h p.i. Blood will be collected in dry Li-Heparin and EDTA tubes (S-Monovette®, Sarstedt). Samples will be analyzed for biochemical and hematological parameters.

-Total body planar scan 3: $t= 24\pm 4h p.i$.

-SPECT/CT scan of 1 region with a cancer lesion: $t= 24.5\pm4h$ p.i. The region will be selected by the PI based on the total body planar scan 3. The PI could decide not to execute a SPECT/CT scan.

-Provide patient with the fourth potassium iodide dose to be taken at 48h \pm 12h after administration of [¹³¹I]-SGMIB Anti-HER2 VHH1.

-Discharge of the patient

5.4 Selection and withdrawal of subjects

5.4.1 Part I (Healthy volunteers)

Inclusion Criteria:

CAMEL-IDS NVBurgemeester EtienneDemunterlaan, 11090 Brusselswww.camel-ids.com

Subjects will only be included in the study if they meet all of the following criteria:

- Subjects who have given informed consent
- Subjects that agree not to drink alcoholic beverages or use any drugs during the study
- Subject with blood parameters within normal ranges
- Age: at least 18 years old

Exclusion Criteria:

Subjects will not be included in the study if one of the following criteria applies:

- Pregnant subjects
- Breast feeding subjects
- Subjects with occupational exposure to ionizing irradiation
- Subjects with clinical significant disease or on concomitant therapy (except contraception)
- Subjects with previous thyroid disorders
- Subjects that received radiolabeled compounds with a long half-life (>7h) for diagnostic or therapeutic purposes within the last 2 days.
- Subjects with absolute contra-indications for thyroid blockage with potassium iodide.
- Subjects with abnormal liver: ALT/AST > 2 times normal values; bilirubin > 1.5 time normal values.
- Subjects with abnormal kidney function: $< 50 \text{ ml/min}/1,73 \text{ m}^2$
- Subjects with recent (< 1 week) gastrointestinal disorders (CTCAE v4.0 grade 3 or 4) with diarrhea as major symptom
- Subjects with any serious active infection
- Subjects who have any other life-threatening illness or organ system dysfunction, which in the opinion of the investigator would either compromise subject safety or interfere with the evaluation of the safety of the test radiopharmaceutical
- Subjects who cannot communicate reliably with the investigator
- Subjects who are unlikely to cooperate with the requirements of the study
- Subjects at increased risk of death from a pre-existing concurrent illness
- Subjects who participated already in this study
- Subjects who participated in a previous trial with Anti-HER2 VHH1

Withdrawal of subjects

The subject may withdraw from the study at any time without giving reasons and without any disadvantageous consequences for his/her subsequent medical care.

The investigator may withdraw a subject from the study at any time in case of intercurrent illness, AE, therapeutic procedure or as a general rule if further participation in the study is believed to be to the subject's detriment.

Any subject withdrawn from the study before the scheduled completion of the study procedures will be considered an early withdrawal, regardless of the reason for withdrawal. For safety

reasons, reasonable attempt should be made to contact withdrawn subjects 24h after the administration of the investigational product to gather information on AEs. For his/her own safety, subjects will be reminded to continue potassium iodide ingestion until 48±12h after administration of [¹³¹I]-SGMIB Anti-HER2 VHH1. Information collected as a result should be recorded on the appropriate case report form (CRF) pages. Subjects withdrawn from the study will be replaced.

Subject recruitment

Healthy subjects will be recruited by the PI using advertising approved by the ethics committee.

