Any patient withdrawn from the study before the scheduled completion of the study procedures will be considered an early withdrawal, regardless of the reason for withdrawal. For safety reasons, reasonable attempt should be made to contact withdrawn subjects 24h after the administration of the investigational product to gather information on AEs. For his/her own safety, subjects will be reminded to continue potassium iodide ingestion until $48\pm12h$ after administration of [¹³¹I]-SGMIB Anti-HER2 VHH1. Information collected as a result should be recorded on the appropriate CRF pages.

Patients withdrawn from the study will be replaced.

Patient recruitment

Patients with HER2+ breast cancer will be recruited by the PI at UZ Brussel and possibly via the ClinicoBru patient recruitment network.

5.5 Clinical Laboratories, Technical Department(s), Institution(s) Providing Clinical Study Services

The local department of clinical chemistry and hematology will perform the clinical laboratory testing of blood samples.

The local nuclear medicine department will provide the analyses of the blood and urine samples:

Whole blood and plasma samples will be counted against appropriate standards of known dilution in an automatic gamma well counter and, after correction for decay and background activity, expressed as a percentage of the injected activity (%IA). The blood volume of each volunteer will be estimated according to body weight and height, using Nadler's formula and the subject's hematocrit

Plasma and urine aliquots will be analyzed by size-exclusion chromatography (SEC) or reverse-

phase high pressure liquid chromatography (RP-HPLC) to identify possible metabolites.

The PI of the local nuclear medicine department will also perform the analyses of the dynamic planar scan, the total body scans and the SPECT/CT scans.

From the dynamic planar scan, time activity curves for kidney and liver activity will be drawn. The total body scans will be used for region of interest analysis to derive input data for the OLINDA/EXM software 1.0 in order to calculate dosimetry data (12).

SPECT/CT scans will be analyzed visually and tumor uptake will be scored by the PI: intense, moderate, low or no uptake. In addition, tumor lesions will be quantified to obtain a measurement of activity per unit of volume.

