6.1 Case report form

6.

A paper CRF will be completed for each screened subject.

This CRF will include specific pages for inclusion and exclusion criteria conclusions, for general and technical examination during the screening visit, and for reporting each visit and biological results. Other specific pages will be dedicated to potential supplementary visit, in case of subject stop or withdrawal, and to the recording of concomitant treatments and AEs (non-serious and serious).

The investigator will review, approve and validate each completed CRF; the investigator's signature (validation) serving as attestation of the investigator's responsibility for ensuring that all clinical and laboratory data entered on the CRF are complete, accurate and authentic.

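### A subject who goes home after Visit 3 and withdraws before Visit 4 holds no potassium iodide, yet the withdrawal rule offers only a reminder to keep taking it

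*Combined protocol and SAP*

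**What the plan says.** Sections 5.3.1 and 5.3.2 set the same regimen for both parts: "potassium iodide dosed as 1 ingestion daily starting 24±6h before" the injection, with the last dose at 48±12h after it. The visit lists assign the doses as follows.

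- Visit 2: dose 1 is taken.
- Visit 3, before injection: dose 2 is taken (for Part II, "Second ingestion of 130 mg potassium iodide"). The post-injection steps end with discharge and include no hand-over of tablets.
- Visit 4, about 24 h: dose 3 is taken (Part I, "Third ingestion of the 130 mg potassium iodide"; Part II, "Third ingestion of 130 mg potassium iodide"), and dose 4 is given out to take at home.

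The row for delivery of thyroid-blocking drugs in Tables 1 and 2 (section 5.13) shows the same pattern, with an entry of 2x under 23.75h.

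For withdrawals, section 5.4.1 asks that a "reasonable attempt should be made to contact withdrawn subjects 24h after the administration of the investigational product to gather information on AEs". It then states: "For his/her own safety, subjects will be reminded to continue potassium iodide ingestion until 48±12h after administration". Section 5.4.2 has the same rule: "subjects will be reminded to continue potassium iodide ingestion until" 48±12h. Section 6.1 provides CRF pages for a "potential supplementary visit, in case of subject stop or withdrawal".

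**The concern.** The protocol itself calls continued blockade a matter of the withdrawn subject's own safety. Its delivery schedule, however, puts both post-injection doses at a visit that a subject who withdraws early will not attend. For that group the instruction cannot be followed from tablets already supplied.

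The exposure is to radioiodine. Part I subjects are healthy volunteers for whom section 5.8.1 expects no benefit, so a safety gap that is easy to close should be closed. No endpoint, analysis or sample-size figure is affected.

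**Working it through.** **Deliveries by visit (Tables 1 and 2, delivery row).** Visit 2: 1. Visit 3, before injection: 1. Visit 4, 23.75h: 2. Sum: 1 + 1 + 2 = 4, which reproduces the total of 4 printed in both tables. The visit lists give the same count, so this is not a misread table.

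**Tablets in hand at Visit 3 discharge.** Delivered so far: 1 + 1 = 2. Taken so far: 2. In hand: 2 − 2 = 0.

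**Doses outstanding.** 4 − 2 = 2, namely dose 3 (about 24 h) and dose 4 (48 − 12 = 36 h to 48 + 12 = 60 h). In milligrams: 2 × 130 = 260 of 4 × 130 = 520. This is the most that can be missed. It is reached only if nothing is supplied after withdrawal.

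**Who is affected, by time of withdrawal after injection.**

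| Withdrawal | Position |
|---|---|
| On site during Visit 3 | Staff can hand over tablets, though the plan does not say so |
| After Visit 3 discharge, before the Visit 4 hand-over | No tablets; reminder only |
| After the Visit 4 hand-over | Not affected |

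**Lead time if the subject is first reached at the 24h contact.** Dose 4: 36 − 24 = 12 h to 60 − 24 = 36 h. Dose 3 is about due. It has no window of its own. If the ±4h of the 23.75h blood samples were borrowed for it (an assumption), it could be taken until 27.75 h, leaving 27.75 − 24 = 3.75 h.

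**Lead time if withdrawal is announced earlier.** The reminder is not tied to the 24h contact. A subject who announces withdrawal at, say, 8 h could be reminded then, 24 − 8 = 16 h before dose 3.

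**Do other provisions fill the gap?** The 24h contact is an attempt, and its stated purpose is adverse-event information. The pages in section 6.1 record a supplementary visit if one takes place; they do not require one or mention dispensing. Visit 1 gives information about potassium iodide, not tablets.

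**The case against.** The strongest reply is that this is a matter of detail. A nuclear medicine department would not remind someone to take tablets without checking that they had them. The 24h contact or a supplementary visit gives an occasion to supply them, and site instructions or subject information may cover it. With 10 subjects the case may never arise. Handing dose 3 to every subject would also weaken supervised dosing for those who complete the study.

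Much of this stands. The plan does not forbid later supply, so a reader might infer that an affected subject will miss both doses; the documents support only that up to two may be missed. A reader might also infer that dose 3 is always lost because contact comes at 24h; that fails when withdrawal is announced earlier. Nor do the documents support a reading that the thyroid is unprotected from injection onward, because dose 2 is taken before injection and covers the first day as planned.

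The reply does not remove the mismatch. The protocol writes a specific safety instruction for withdrawn subjects and a specific delivery schedule, and for this group the two do not fit together. The concern about supervised dosing is fair and is a reason to offer an alternative fix.

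**Conclusion.** The point holds and is minor. A subject who withdraws between Visit 3 discharge and the Visit 4 hand-over holds no study-supplied potassium iodide, and the available text names no step to supply it. Unless the site acts on its own initiative, up to 2 of 4 doses (260 of 520 mg) may be missed.

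The number affected is likely very small: 10 subjects are planned, and withdrawal must fall in one interval between two visits. The documents give no withdrawal rate, free-iodide fraction or thyroid uptake, so neither the expected number nor the thyroid dose can be estimated, and no harm is asserted.

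The conclusion rests on the visit lists, both tables and both withdrawal paragraphs, which agree. The front pages, the consent pages and some text around section 5.7 are missing from the public copy, so a supply instruction there cannot be excluded.

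**What to change.** **Preferred.** Give doses 3 and 4 to the subject at Visit 3 discharge. Move the 2x entry in the delivery row of Tables 1 and 2 from 23.75h to the end of Visit 3, and align the Visit 3 and Visit 4 text in sections 5.3.1 and 5.3.2. Returning subjects bring dose 3 and take it on site at Visit 4 as now, with a spare held on site.

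**Alternative, if delivery stays at Visit 4.** Add to sections 5.4.1 and 5.4.2 that remaining potassium iodide is dispensed to any subject who withdraws after injection, either on site or through a named pick-up or delivery route.

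**Cost.** The preferred change touches two visit lists and two table rows, and needs a spare tablet on site. The alternative is one sentence in each of two paragraphs, plus the named supply route. Neither adds a scheduled study visit or changes the number, size or timing of doses. The downside of the preferred change is that dose 3 may occasionally be forgotten or taken unsupervised at home; dose 4 is already taken at home.
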